5.3.1.1.3 Handling of missing data

The number of missing values by visit for the main secondary efficacy endpoint will be provided using descriptive statistics on the mITT. Additionally, the number of missing values by visit due to COVID-19 will be summarized for the main secondary efficacy endpoint (using the “COVID-19 Impact” e-CRF page) as explained in Section 5.2.

For secondary efficacy analyses, missing data will be handled according to the secondary efficacy estimand definition:

- For missing data of participants that discontinue from the study, a missing at random assumption will be used for imputation.
- For other missing data, the same missing at random assumption as the one used for imputing missing data of participants that discontinue from the study will be applied.

The MMRM that will be used to model the CFB to Week 12 in MG-ADL score consider missing data with the missing at random assumption.

5.3.1.1.4 Sensitivity analysis

The one-sample t-test will be applied on the observed data at Week 12.

A one-sample Wilcoxon Signed Rank Test will also be applied on the observed data at Week 12, with Worst observation carried forward between baseline and all post baseline visits.

5.3.1.2 Additional secondary efficacy endpoint

5.3.1.2.1 Definition of endpoint

The additional secondary efficacy endpoint is the CFB in Week 12 in QMG Score. More details on how these scores are calculated can be found respectively in Section [6.1.5.2](#).

5.3.1.2.2 Main analytical approach

For the additional secondary efficacy endpoint, the same strategy (main analytical approach in Section [5.3.1.1.2](#) and handling of missing data in Section [5.3.1.1.3](#)) will be applied.

No statistical test will be performed for the additional secondary efficacy endpoint.

5.3.2 Other efficacy endpoint analyses

The other efficacy endpoints are:

- Time to first receipt of rescue therapy over the Main Treatment Period
- Change in SoC therapy medication dose regimen for gMG during the Main Treatment Period
- Achievement of Minimal Manifestation Status per MGFA PIS at Week 12 without rescue therapy
- Achieving MSE, defined as an MG ADL of 0 or 1 at Week 12 without rescue therapy
- CFB to Week 12 in QMG subscores: ocular, bulbar, respiratory, limb
- CFB to Week 12 in MG-QOL15r score
- MG-ADL score responder rate (responder is defined as achieving ≥ 3 -point improvement from Baseline [decrease] at Week 12 and not having taken rescue therapy)
- QMG score responder rate (responder is defined as achieving ≥ 5 -point improvement from Baseline [decrease] at Week 12 and not having taken rescue therapy)

The MG-ADL score responder rate will be assessed based only on participants having an MG-ADL score ≥ 3 at Baseline, while the QMG score responder rate will be assessed based only on participants having an QMG score ≥ 5 at Baseline.

All those endpoints will be analyzed using descriptive statistics, as mentioned in the Section [5.1](#).

The time to first receipt of rescue therapy over the Main Treatment Period and over the Overall Treatment Period will be analyzed as time-to-event, using Kaplan-Meier plots.

For the MG-ADL and QMG responder rate the number and percentage of participants who have a reduction (i.e., improvement) of $\geq X$ will be summarized in the mITT at Week 12. The improvement values will start at the maximum level of worsening and will continue to the maximum level of improvement seen in the study. Note this is an extension of the “Achieving a ≥ 3 -point reduction in MG-ADL Score at Week 12 without rescue therapy” and “Achieving a ≥ 5 -point reduction in QMG Score at Week 12 without rescue therapy” endpoints.

Individual line plots with individual values of Total MG-ADL, QMG and MG-QoL15r scores will be created in mITT.

For participants infected with COVID-19 as per the AE page, CFB in QMG and MG-QOL15r score will be listed by visit separately.

5.4 Planned safety and other analyses

Safety analyses will be presented on the SS. Listings for all safety analyses will be presented.

5.4.1 Extent of Exposure

IMP duration will be summarized. The number of days on IMP will be calculated as follows:

$$\text{IMP duration} = [(\text{Date of Last Dose Received}) - (\text{Date of First Dose Received})] + 1$$

The exposure duration (i.e., total time at risk that incorporates 5 half-lives of ZLP) is defined as:

$$\text{Exposure duration (in days)} = [\min (\text{Last dose} + 40 \text{ days}, \text{Last Visit/Contact}) - (\text{Date of First Dose Received})] + 1$$

Patient-years exposure (PEY) will be calculated as the sum of the exposure durations of all study participants divided by 365.25.

The overall extent of exposure in the SS will be summarized during the Main Treatment Period and in the Overall Treatment Period.

Note that temporary drug discontinuations and missed doses will not be incorporated into the calculations of the extent of study drug exposure analyses.

The number of doses missed (from the eCRF Study drug administration page after Day 1) will be summarized cumulatively. The missed doses will be derived based on the expected number of daily doses the participant should receive within a defined period minus the total number of doses he/she has received during that period. For this derivation, the number of total syringes administered to a participant at each visit will be considered via the total number of kits administered at each visit, assuming that each kit contains 7 syringes to be used for 7 daily doses.

In addition to the assessment of study medication duration as a continuous variable, the number and percent of study participants with treatment duration meeting the following criteria will also be summarized:

- ≥ 1 day
- ≥ 8 days
- ≥ 15 days
- ≥ 29 days
- ≥ 57 days
- ≥ 84 days

All drug administration details will be listed.

The compliance between two in-clinic visits, as well as the overall compliance will be described.

The study withdrawal will be summarized over the Main Treatment Period and over the Overall Treatment Period time-to-event, using Kaplan-Meier plot.

For the Main Treatment Period, time to IMP discontinuation is defined as: Date of last IMP dose – date of first IMP dose + 1. Participants that did not early withdraw should be censored at the date of Main Treatment Period completion.

For the Overall Treatment Period, time to IMP discontinuation is defined as: Date of last IMP dose – date of first IMP in Main Treatment Period + 1. Participants that did not (early) withdraw should be censored at the date of their last contact.

For the Extension Treatment Period, time to IMP discontinuation is defined as: Date of last IMP dose – date of first IMP in Extension Treatment Period+ 1. Participants that did not withdraw should be censored at the date of their last contact.

For all treatment periods, participants that switch to commercially available Zilucoplan are not considered as discontinuation events; for the time to event analysis exposure will be censored at the date of their last contact.

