**Table 1-2: Schedule of Activities**

Study Period	Screening Period a	Main Treatment Period						Extension Treatment Period	EW/ Withdrawal Visit b,w	SFU Visit (In-clinic) c	Rescue Therapy Visit (If applicable) d
		Baseline e (In-clinic)	Week 1 (Phone call)	Week 2 (In-clinic)	Week 4 (Phone call)	Week 8 (Phone call)	Week 12 (In-clinic)				
Visit name	Screening Visit (In-clinic)							Week 24, 36, 48... every 12 weeks (In-clinic)			
Visit #	1	2	3	4	5	6	7	8, 9, 10...	–	–	–
Day	-14 or -56	1	8	15	29	57	84	168, 252, 336...		(Last dose +40 days)	
Visit Window f	±3d	±2d	±2d	±2d	±2d	±2d	±2d	±7d		±7d	
Procedure/activity											

f The visit windows provided are with respect to the Baseline Visit with the exception of the SFU Visit, in which the visit window applies to 40 days after the last dose of study medication.

g Procedures performed as SOC during the Screening Period may be used to determine eligibility. Informed consent must be obtained prior to performing any study-specific procedures that are not SOC.

h Screening includes disease history with documented diagnosis of gMG by the MGFA criteria (Class II-IVa) and documented serology for AChR autoantibodies.

i Height will be measured only at Screening.

j All prescriptions and over-the-counter medications taken during the 30 days prior to Screening through the last study visit will be documented. Note: A complete history of medications taken for the treatment of gMG will be collected.

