### **6.2.1 Drug accountability**

The eCRF will be used to record study medication dispensing and return information on a by-participant basis and will serve as source documentation during the course of the study. Details of any study medication lost, damaged (due to breakage or wastage), not used, partially used, disposed of at the study site, or returned to the Sponsor or designee must also be recorded on the appropriate forms. All supplies and pharmacy documentation must be made available throughout the study for UCB (or designee) to review.

The Investigator (or designee) is responsible for retaining all used, unused, and partially used containers of study medication until returned or destroyed.

The Investigator may assign some of the Investigator's duties for drug accountability at the study site to an appropriate pharmacist/designee.

The Investigator must ensure that the study medication is used only in accordance with the protocol.

Periodically, and/or after completion of the clinical phase of the study, all used (including empty containers/partially used), unused, damaged, and/or expired study medication must be reconciled and either destroyed at the site according to local laws, regulations, and UCB standard operating procedures (SOPs) or returned to UCB (or designee). Study medication intended for the study cannot be used for any other purpose than that described in this protocol.

For further details about drug accountability, refer to the IMP Handling Manual.

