Section 6.2.1 Laboratory Assessments Marked Abnormality Criteria	
 Text labs from Table 6-6 Laboratory Abnormalities: Calcium, Albumin, CRP and GGT labs are deleted 	
 According to the study protocol, albumin, CRP and GGT are not collected. Calcium as parameter of abnormalities is checked via the Corrected Calcium which cannot be derived in the study.
6.3 Appendix 3: Changes to Protocol- Planned Analyses	
Deleted text:
 
The Screened Set population has been added to ease the display of some descriptive statistics.
	Screen Set has been deleted from the SAP Amendment 2

Amendment 3.0

The purpose of the SAP amendment 3.0 is to make the changes as listed in the table below.

The table below does not include correction of minor typographical errors and formatting/stylistic changes.

Section # and Name	Description of Change	Brief Rationale
Section 5.1.1.10 Handling of missing dates and times	The following crossed-out text is deleted: Discharge date refers to the date of the end of study visit for completed or the date of discontinuation for participants that were withdrawn.	To remove the redundant text, as the date of discontinuation for withdrawn participants is captured in the eCRF in the safety follow up visit.
Section 5.4.1 Extent of Exposure	
 The following text is added: "The missed doses will be derived based on the expected number of daily doses the participant should receive within a defined period minus the total number of doses he/she has received during that period. For this derivation, the number of total syringes administered to a participant at each visit will be considered via the total number of kits administered at each visit, assuming that 	
 The number of missed doses are not collected in the eCRF and should be derived. Added text is to document that the number of missed daily doses will be derived based on the number of administered kits vs number of returned syringes. This derivation

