6.1.8 Extent of Exposure

The time to study withdrawal is defined as Date of study withdrawal – date of first IMP + 1.

The compliance between 2 clinic visits will be calculated as: (number of syringes dispensed at the previous clinic visit – number of unused syringes returned in clinic – total number of malfunctioned syringes)/(Date the syringes are returned in clinic – Date the syringes are dispensed in clinic)*100.

The overall compliance in the Main Treatment Period will be calculated as: (total number of syringes dispensed – total number of unused syringes – total number of malfunctioned syringes) / (Date the last syringes are returned in clinic in the Main Treatment Period – Date the first syringes are dispensed in clinic)*100.

For participants entering in the Extension Treatment Period, the overall compliance in the Overall Treatment Period will be calculated as: (total number of syringes dispensed – total number of unused syringes – total number of malfunctioned syringes+1)/(Date of last drug administration – Date the first syringes are dispensed in clinic in the Main Treatment Period+1)*100.

If the participant was (early) withdrawn, then the date to be considered in the calculation of compliance as the end of exposure period will be the date of last administration of Zilucoplan and not the date the participant returned the syringes in clinic. Then, the compliance will be calculated as follows: (number of syringes dispensed at the previous clinic visit – number of unused syringes returned in clinic – total number of malfunctioned syringes+1)/(Date of last drug administration – Date the syringes are dispensed in clinic + 1)*100.

Of note, the number of syringes dispensed at each visit will be derived based on the number of kits dispensed at that visit, assuming that each kit contains 7 single dose syringes to be used for the daily dosing.

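### SAP 5.4.1 takes doses received as seven per kit without subtracting unused or malfunctioned syringes, so its missed-dose count, applied literally, cannot register a missed dose and disagrees with the compliance formula in 6.1.8

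*SAP*

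**What the plan says.** Three statements in SAP 5.4.1 (Extent of Exposure) bear on missed doses.

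- The source: "The number of doses missed (from the eCRF Study drug administration page after Day 1) will be summarized cumulatively".
- The definition: the expected number of daily doses in a period, "minus the total number of doses he/she has received during that period".
- The counting rule: "the number of total syringes administered to a participant at each visit will be considered via the total number of kits administered" at each visit, with seven syringes to a kit. The section has no term for syringes that came back unused or that malfunctioned.

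SAP 6.1.8 makes the same conversion for compliance: "the number of syringes dispensed at each visit will be derived based on the number of kits dispensed at that visit", again at seven per kit. It then subtracts the "number of unused syringes returned in clinic" and the malfunctioned syringes before dividing by days. In the Overall Treatment Period formula and the formula for withdrawn participants, it also adds one to both numerator and denominator.

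The SAP version history, in the Amendment 3.0 rationale for the 5.4.1 text, says that missed doses are not collected in the eCRF and are to be derived "based on the number of administered kits vs number of returned syringes". Protocol 6.2.1 states: "The eCRF will be used to record study medication dispensing and return information on a by-participant basis".

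**The concern.** A count of missed doses has to depend on how many doses were taken. The rule in 5.4.1 depends only on how many kits were handed out. I read kits administered as kits dispensed. Kits are given out for daily self-injection at home, and 6.1.8 uses dispensed for the same conversion.

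If the rule is programmed as written, an adequately supplied participant shows no missed dose whatever happened. The compliance figure for the same interval may show otherwise. A negative count would be noticed in checking. A zero would not, because it looks like perfect adherence.

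**Working it through.** The documents state no missed-dose figure, so there is none to reproduce. The check compares the two rules.

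**Inputs**
- Seven syringes per kit (SAP 5.4.1 and 6.1.8; Protocol Table 6-1).
- Visit days 1, 15 and 84 for Baseline, Week 2 and Week 12, each ±2 days (Protocol Table 1-2, where "The visit windows provided are with respect to the Baseline Visit").
- Kits dispensed (K), unused syringes (U) and malfunctioned syringes (M) are assumed, because the documents do not give them.

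**Formulas**, with N the expected doses:
- 5.4.1 read literally: missed = N − 7K.
- Using the between-visit or Main Treatment Period numerator of 6.1.8: missed = N − (7K − U − M) = N − 7K + U + M.
- Difference: the literal rule is too low by U + M, whatever K is. Where 6.1.8 adds one to the numerator, the gap is U + M − 1.

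**Range of the literal rule.** The fewest kits that cover N doses is N/7 rounded up, so the result lies between 0 and −6. From Week 2 to Week 12 the nominal interval is 84 − 15 = 69 days. The windows allow 82 − 17 = 65 to 86 − 13 = 73 days.
- 10 kits, N = 65 to 70: −5 to 0.
- 11 kits, N = 71 to 73: −6 to −4.
- 11 kits for everyone, N = 65 to 73: 65 − 77 = −12 to 73 − 77 = −4.

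**Illustrations** (N is the 6.1.8 denominator, a difference of dates)

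| Interval | N | K | U | M | 5.4.1 literal | 7K − U − M | Missed, 6.1.8 basis | Compliance |
|---|---|---|---|---|---|---|---|---|
| Baseline to Week 2 | 14 | 2 | 3 | 0 | 0 | 11 | 3 | 11/14 = 78.6% |
| Week 2 to Week 12 | 69 | 10 | 10 | 0 | −1 | 60 | 9 | 60/69 = 87.0% |
| Week 2 to Week 12 | 69 | 11 | 17 | 0 | −8 | 60 | 9 | 60/69 = 87.0% |
| Day 1 to Day 84 | 83 | 12 | 1 | 0 | −1 | 83 | 0 | 83/83 = 100% |
| Day 1 to Day 84 | 83 | 12 | 11 | 0 | −1 | 73 | 10 | 73/83 = 88.0% |
| Day 1 to Day 84 | 83 | 12 | 9 | 2 | −1 | 73 | 10 | 73/83 = 88.0% |
| Day 1 to Day 84 | 83 | 12 | 21 | 0 | −1 | 63 | 20 | 63/83 = 75.9% |

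Over Day 1 to Day 84 with 12 kits, the literal rule gives −1 whether 0, 10 or 20 doses were missed. It is positive only when supply falls short: 11 kits over 83 days give 83 − 77 = 6.

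**Early withdrawal.** Suppose 10 kits are dispensed on Day 15 and the last dose is on Day 30. The 6.1.8 denominator is 30 − 15 + 1 = 16, and the literal rule gives 16 − 70 = −54. With 55 syringes returned unused, the 6.1.8 numerator is 70 − 55 + 1 = 16, so compliance is 100% and missed doses are 16 − 16 = 0. Using that denominator with a numerator that lacks the +1 would give 16 − 15 = 1, a spurious missed dose. The correction must therefore take numerator and denominator from the same formula.

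**The case against.** The strongest reply is that N − 7K is not what the authors meant. The definition speaks of doses received. The kit sentence can be read as no more than the conversion from kits to syringes, as in the last sentence of 6.1.8. The Amendment 3.0 rationale names returned syringes outright. This stands as evidence of intent, and a reader should not infer that the plan deliberately counts every dispensed syringe as taken. It does not supply the missing step: the rationale sits in the version history and mentions returned syringes but not malfunctioned ones. The operative section gives a counting rule that omits both. The separate table specifications might state the step, but they are not among the documents.

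A reader might also infer that 5.4.1 names two conflicting data sources, an eCRF page and a kit derivation. The text does not go that far. The parenthesis can be read as naming where the raw data sit, with the following sentences saying how the count is derived from them. It is loose wording that needs tidying.

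A third inference would be that exposure or the safety results are compromised. They are not. SAP 5.4.1 keeps missed doses out of the exposure calculations and lists all drug administration details. Nothing in the documents feeds this count into the primary safety endpoints, the MG-ADL test or the analysis sets. Site staff also record at every visit whether doses were missed (Protocol 6.4).

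**Conclusion.** The point holds as a minor defect in a stated rule. Applied literally, 5.4.1 gives N − 7K. This is zero or negative whenever supply covers the period, does not respond to missed doses, and differs from the between-visit and Main Treatment Period numerators of 6.1.8 by exactly U + M. The algebra needs no assumption beyond reading kits administered as kits dispensed. The sizes in the examples depend on assumed kit and return counts. The two sections agree when no syringe is unused or malfunctioned, apart from the +1 in the Overall and withdrawn formulas. It is most likely a drafting omission, and its effect is confined to the descriptive missed-dose summary.

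**What to change.** In SAP 5.4.1, set doses received in a period equal to the numerator of the 6.1.8 compliance formula for that period and participant. That is seven times the kits dispensed, minus unused syringes, minus malfunctioned syringes, with the +1 wherever 6.1.8 applies it. Set expected doses equal to the denominator of the same formula. Missed doses are then denominator minus numerator, and compliance is numerator over denominator, so the two summaries must agree. Reword the parenthesis about the eCRF page so that it names the source data for this derivation.

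The cost is one sentence and one rewording. No new data are needed, because dispensing and return counts are already recorded under Protocol 6.2.1 and used in 6.1.8. One small limitation remains, shared with 6.1.8: a syringe that is lost and not returned counts as taken.

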## **6.8 Treatment after the end of the study**

At the conclusion of the Main Treatment Period, study participants will have the option to continue ZLP treatment in the Extension Treatment Period, during which SC ZLP will continue to be provided until the approval of the marketing application for the indication of gMG in the US or until further notice from the Sponsor.

If at the end of the Main Treatment Period a study participant chooses not to participate in the Extension Treatment Period, the participant will complete an SFU Visit 40 days ( $\pm 7$  days) after the last dose of study medication and receive SOC treatment off-study, as recommended by the treating physician.

If during the Extension Treatment Period a study participant discontinues ZLP, he/she will transition to SOC treatment off-study as recommended by the treating physician. These participants will complete a Withdrawal Visit and a SFU Visit 40 days ( $\pm 7$  days) after the last dose of study medication.

If a participant is in the Extension Treatment Period at the time ZLP becomes commercially available, he/she will transition to ZLP treatment outside of the study. He/she will complete a Withdrawal Visit and will not need to complete a SFU Visit. If by the time a participant completes the Main Treatment Period ZLP is commercially available, the participant may transition to commercially available ZLP directly following the Week 12 visit at the end of the Main Treatment Period.

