All study participants who complete the Main Treatment Period will have the option to continue ZLP treatment in the Extension Treatment Period after the Week 12 visit. If a study participant withdraws from the study during the Main Treatment Period, the participant will complete an Early Withdrawal (EW) Visit followed by a SFU Visit 40 days (± 7 days) after the last dose of study medications. Participants who opt not to continue into the Extension Treatment Period will complete a SFU Visit 40 days (± 7 days) after the last dose of study medication.

The Extension Treatment Period consists of in-clinic visits every 12 weeks (± 7 days) and will continue until all participants are withdrawn, until ZLP is approved and available in the US, or until further notice from the Sponsor. During these visits, ZLP accountability and resupply will be performed, medications updated, and safety will be assessed. Participants who withdraw or discontinue ZLP during the Extension Treatment Period will complete a Withdrawal Visit followed by a SFU Visit 40 days (± 7 days) after the last dose of study medication. Participants who transition to commercially available ZLP will complete a Withdrawal Visit but will not require a SFU Visit. If by the time a participant completes the Main Treatment Period ZLP is commercially available, the participant may transition to commercially available ZLP directly following the Week 12 visit at the end of the Main Treatment Period.

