5.1.1.1.3 Study periods

Based on the specific requirements of safety and efficacy analyses, one concept of the definition of periods need to be considered for the study, which will be defined in detail in the section below.

5.1.1.1.3.1 Study periods for safety and efficacy data

- Two study periods are included in this study, the Main Treatment Period and the Extension Treatment Period.

No efficacy data are collected during the Extension Treatment Period thus, for efficacy analyses, only the Main Treatment Period will be considered.

The safety analyses will be performed on the Main Treatment Period as well as on the Overall Treatment Period. The Overall Treatment Period is constituted of the Main Treatment Period and of the Extension Treatment Period. The following definitions for completing study periods will be applied:

- A participant is considered to have completed the Main Treatment Period if he/she completed the Week 12 visit and:
 - Decided to enter the Extension Treatment Period.
 - OR
 - Transitioned to commercially available ZLP directly after the Week 12 visit (no Withdrawal or SFU visit required).
 - OR
 - Decided not to enter the Extension Treatment Period and completed a SFU visit.
- A participant is considered to have completed the study if he/she completed the Main Treatment Period and:
 - Did not enter the Extension Treatment Period.
 - OR
 - Entered the Extension Treatment Period and:
 - withdrew from the Extension Treatment Period, discontinued ZLP, and completed the Withdrawal and SFU Visits.
 - transitioned to commercially available ZLP and completed the Withdrawal Visit. No SFU Visit is required.

The total duration of study participation in the Main Treatment Period for all participants will be up to approximately 20 or 26 weeks, including the following periods:

- Screening Period: 2 to 8 weeks
- Treatment Period: 12-weeks
- SFU Period: 40 days (after the last dose for patients who do not enter the extension period or do not transition to commercially available ZLP directly after the Week 12 visit).

The Extension Treatment Period is constituted of the following periods:

- Treatment period
- SFU period: 40 days, for participants that withdrew from the Extension Treatment Period

The end of the study is defined as the date of the last visit of the last participant in the study.

The following definitions for starting and entering the periods will be applied:

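### The Overall Treatment Period curve of time to IMP discontinuation does not count participants who stop zilucoplan at Week 12 by declining the Extension, and keeps them at risk for about 40 days off drug

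*SAP*

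**What the plan says.** For the Overall Treatment Period, SAP 5.4.1 states: "time to IMP discontinuation is defined as: Date of last IMP dose – date of first IMP in Main Treatment Period + 1". The next sentence sets the censoring: "Participants that did not (early) withdraw should be censored at the date of their last contact". One exception is written for all periods: "participants that switch to commercially available Zilucoplan are not considered as discontinuation events"; they are censored at last contact. No sentence deals with a participant who finishes Week 12 and declines the Extension.

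The status of that participant follows from SAP 5.1.1.1.3. One way to complete the Main Treatment Period is "Decided not to enter the Extension Treatment Period and completed a SFU visit". One way to complete the study, given completion of the Main Treatment Period, is "Did not enter the Extension Treatment Period". Protocol 4.4 has the same definitions. On visits, SAP 1.2 says: "Participants who opt not to continue into the Extension Treatment Period will complete a SFU Visit 40 days" after the last dose. It asks for no Early Withdrawal or Withdrawal Visit. Protocol 6.8 says that these participants will "receive SOC treatment off-study, as recommended by the treating physician". For those who stop later, SAP 1.2 says: "Participants who withdraw or discontinue ZLP during the Extension Treatment Period will complete a Withdrawal Visit".

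SAP 5.4.1 also defines a separate Extension Treatment Period curve, timed from the first dose in the Extension.

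**The concern.** The quantity named is discontinuation of the drug, and its clock stops at the last dose. The event indicator depends on something else, namely withdrawal. For most participants the two agree. They part for one group: completers who decline the Extension and do not move to commercial zilucoplan. These participants stop the drug and are not events.

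The result is inconsistent at the boundary. Someone who enters the Extension and stops the next day is an event at about Day 85. Someone who stops at Week 12 is censored at about Day 124. Completer status does not explain the difference, because a participant who leaves the Extension and attends the Withdrawal and Safety Follow-up Visits is also defined as having completed the study.

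The censoring date adds a second fault. Events are timed at last dose and censoring at last contact. A decliner therefore stays in the risk set for about 40 days, at risk of stopping a drug already stopped.

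At stake is how the curve reads after Week 12. The Extension curve does not repair this: decliners have no Extension dose and so are not in it. No curve that runs beyond Week 12 counts them.

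**Working it through.** The plan states no figure for this curve. Its one design figure is the power for the MG-ADL test: 20 participants, SD 3, margin 2, true change 0, 1-sided 0.025. It reproduces as 80.7% by the one-sample t-test (noncentrality 2/(3/√20) = 2.98, 19 degrees of freedom), against about 80% stated. The point does not depend on it.

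Inputs from the documents:
- 20 participants planned (Protocol 9.8).
- Week 12 visit on Day 84 (Protocol Table 1-2).
- Safety Follow-up Visit 40 ± 7 days after the last dose (SAP 1.2).

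Assumptions: all 20 are treated; decliners take their last dose on Day 84 and attend the Safety Follow-up Visit; nobody is censored before Week 12. A decliner's last contact is then Day 84 + 40 = 124 (range 84 + 33 = 117 to 84 + 47 = 131). The number of decliners, *d*, and the numbers and dates of other stops are also assumed, because the documents give none.

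**Step 1, just after Week 12.** With *w* withdrawals in the Main Treatment Period, the SAP rule gives (20 − w)/20 for any *d*. Counting decliners as events at last dose gives (20 − w − d)/20. The difference is d/20, or 5 points per decliner.

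| d | w = 0: SAP rule | w = 0: decliners as events | w = 2: SAP rule | w = 2: decliners as events |
|---|---|---|---|---|
| 0 | 100% | 100% | 90% | 90% |
| 1 | 100% | 95% | 90% | 85% |
| 2 | 100% | 90% | 90% | 80% |
| 4 | 100% | 80% | 90% | 70% |
| 6 | 100% | 70% | 90% | 60% |

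**Step 2, later in the Extension.** Keep w = 2 and add two Extension stops, on Days 100 and 200. On Day 100 the decliners are still in the SAP risk set of 18; by Day 200 they have left it.
- SAP rule at Day 252: (18/20) × (17/18) × (16 − d)/(17 − d).
- Decliners as events: (16 − d)/20.

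| d | SAP rule | Decliners as events |
|---|---|---|
| 0 | 80% | 80% |
| 1 | 79.7% | 75% |
| 2 | 79.3% | 70% |
| 4 | 78.5% | 60% |
| 6 | 77.3% | 50% |

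**Step 3, effect of censoring at last contact.** Take w = 0, d = 4 and two Extension stops. If both fall after Day 124, the SAP curve ends at 14/16 = 87.5%. If both fall before Day 124, the decliners are still in the denominator and it ends at 18/20 = 90%. With decliners as events it ends at 14/20 = 70% in both cases.

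**The case against.** The strongest reply is that the curve is meant to show withdrawal. SAP 5.4.1 introduces the plot as a summary of study withdrawal, the discontinuation definitions follow directly, and event status is tied to withdrawal. Censoring someone who finished the planned 12 weeks is then correct. The Extension is optional and was added to give access to the drug (Protocol 4.2), and no listed objective concerns persistence.

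This stands in part. The documents set no persistence estimand, and retitling would be a legitimate remedy. It does not rescue the present text. The variable is named for IMP discontinuation and ends at the last dose, whereas SAP 6.1.8 defines time to study withdrawal separately, ending on the withdrawal date. Even for a withdrawal curve, 40 off-drug days of follow-up sit oddly beside events timed at last dose.

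Four further limits are fair:
- The disposition summary (SAP 5.2) gives the numbers who completed the Main Treatment Period and who entered the Extension. A reader can largely infer how many declined, although direct movers to commercial zilucoplan must be separated out.
- A reader might infer that the Overall curve is the only view of continued use beyond 12 weeks. It is not: there is an Extension curve, and IMP duration is summarised.
- A reader might infer that the censoring is informative because decliners disliked the drug or did not benefit. The documents give no reasons for declining. The mismatch in event status does not depend on the reason.
- The rule for commercial switchers is explicit and reasonable, since they remain on zilucoplan.

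**Conclusion.** The point holds as a mismatch between what the Overall curve is called and what it counts. As written, the curve cannot fall at Week 12 because of decliners. It sits 5 percentage points per decliner above the proportion still on drug just after Week 12, given 20 treated and no censoring before then. The later gap depends on when Extension stops fall relative to the decliners' last contact. The number of decliners is unknown; with none, the two rules agree.

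A reader might go further and infer that the study's safety conclusions are affected. The documents do not support that. The curve is a descriptive exposure display. The primary safety endpoints and the study-withdrawal endpoint are confined to the Main Treatment Period, and the only planned test is on MG-ADL. The point covers decliners who attend the Safety Follow-up Visit; the completion definitions do not settle the status of those who do not attend.

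**What to change.** In SAP 5.4.1, for the Overall Treatment Period curve, count a participant who stops zilucoplan at Week 12 without moving to commercial zilucoplan as an event on the date of last dose, and show the number of decliners with the curve.

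If the sponsor instead intends time to (early) withdrawal, retitle the curve accordingly, censor decliners at the date of last dose and not at last contact, and report their number beside it.

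The existing non-event rule for commercial switchers can stay in either case. The cost is a change of SAP wording and of one derivation, using dates that the analysis already needs. If anyone declines, the first option makes the curve less favourable.
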